6.2.1 Additional analyses

All analyses mentioned above will additionally be performed by dose actually received. It should again be noted that these analyses must be interpreted carefully, as only the dose actually received in Part A can be assumed to be independent of the efficacy. For all other parts the dose actually received depends on post-baseline events.

In addition to the number of bleed endpoints already mentioned, annualized bleed rates will be provided and analyzed. It should be mentioned that the parts of the study have a planned length of three months, and that a subject being initially assigned to the highest dose will have a planned follow-up of 6 months until the primary completion. Thus for an annualization an extrapolation is needed which makes the interpretation of this endpoint in a literal sense imprecise. However, the annualized bleed rate is considered useful and will be included, as this type of endpoint accounts for the possible different follow-up length of subjects (including drop-outs).

CCI
[Redacted]

The annualized bleed rate will be derived as follows:

Annualized bleed rate for Part A is defined as

$$\frac{(\# \text{ of bleeds in Part A}) \cdot 365.25}{(\text{last datetime in Part A} - \text{first datetime in Part A}) \cdot 60 \cdot 60 \cdot 24}$$

Annualized bleed rate for each 12-week Part B period is defined as

$$\frac{(\# \text{ of bleeds in Part B}) \cdot 365.25}{(\text{last datetime in Part B} - \text{first datetime in Part B}) \cdot 60 \cdot 60 \cdot 24}$$

Annualized bleed rate for period on dose initially received (DIR) is defined as

$$\frac{(\# \text{ of bleeds in period on DIR}) \cdot 365.25}{(\text{last datetime on DIR} - \text{first datetime on DIR}) \cdot 60 \cdot 60 \cdot 24}$$

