Document Type:	Statistical Analysis Plan
Official Title:	Multiple escalating dose study of BAY 1093884 in adults with hemophilia A or B with or without inhibitors
NCT Number:	NCT03597022
Document Date:	10-MAR-2020

Title page

Study Protocol Title (incl. version no. and date): Multiple escalating dose study of BAY 1093884 in adults with hemophilia A or B with or without inhibitors, Version 2.0, dates 26 Jun 2018

SAP (incl. Version no. and date): 1.0, dated 23 Jul 2018

Analysis purpose: Post-hoc analyses

Clinical study phase: 2 **Date:** 10 MAR 2020

Study No.: 19580 **Version:** 1.0

Author: PPD

Confidential

The information provided in this document is strictly confidential and is intended solely for the guidance of the clinical investigation. Reproduction or disclosure of this document, whether in part or in full, to parties not associated with the clinical investigation or its use for any other purpose without the prior written consent of the sponsor is not permitted.

Throughout this document, symbols indicating proprietary names (®, TM) are not displayed unless quotations from other documents are given. Hence, the appearance of product names without these symbols does not imply that these names are not protected.

This "Additional Statistical Analysis Plan" is produced on a word-processing system and bears no signatures.

**Additional Statistical Analysis Plan
for abbreviated CSR**

Preamble

This Statistical analyses plan is for the documentation of post-hoc analyses for publishing purposes.

Table of Contents

Title page.....1

1. Annualized Bleeding rates.....3

2. Individual Lab plot3

3. PK/PD individual plots3

1. Annualized Bleeding rates

The number of bleeds and annualized bleeding rate is shown by treatment arm. The table differentiates the bleeds into all bleeds and spontaneous bleeds. In addition, these bleeds are separated by treated and untreated bleeds. For the number of bleeds the 24 hours rule as well as the 72 hours rule as described in SAP sections 4.5.3 and 4.5.4 apply. Use SAS code from Kovaltry and/or Jivi as reference.

The annualized bleeding rate is defined as

$$\frac{(\# \text{ of bleeds in data scope time}) \cdot 365.25}{(\text{last date in data scope} - \text{first date in data scope} + 1)}$$

The following data scopes will be analysed:

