- Bleeds in 6 months before randomization. The last date of data scope is the day of randomization, the first date in data scope is 6 months before, i.e. the time in the data scope is fixed at 183 days. This bleeds will be shown by dose initially received.
- Dose initially given: First date in that data scope is defined as first intake of the study treatment. Last date is the date of the intake of any study drug. Show bleeds for combined Part A and Part B (whole study time), as well as for Part A (last date is the end of Part A in this case) and Part B (first date is the start of Part B in this case).
- Dose actually given: show for the dose actually given the annualized bleeding rates in Part B - for patients that get escalated in Part B the last date in the data scope for a specific dose is the day the escalation into the higher dose group. For these patients the first day is the new dose group is the first date of the data scope for Part B and that escalated dose group is the day of the escalation.

Subgroup analyses will be performed by previous treatment.

2. Individual Lab plot

Show table CLIPS LB1C and figure CLIPS LB-F2 for available laboratory parameter and subjects.

3. PK/PD individual plots

Show figure CLIPS PK-F2 for available PK/PD parameter.

Title page**Multiple escalating dose study of BAY 1093884 in adults with hemophilia A or B with or without inhibitors****Bayer study drug** BAY 1093884**Clinical study phase:** 2 **Date:** 23 Jul 2018**Study No.:** 19580 **Version:** 1.0**Author:** PPD **Confidential**

The information provided in this document is strictly confidential and is intended solely for the guidance of the clinical investigation. Reproduction or disclosure of this document, whether in part or in full, to parties not associated with the clinical investigation or its use for any other purpose without the prior written consent of the sponsor is not permitted.

Throughout this document, symbols indicating proprietary names (®, TM) are not displayed. Hence, the appearance of product names without these symbols does not imply that these names are not protected.

This Statistical Analysis Plan is produced on a word-processing system and bears no signatures.

The approval of the Statistical Analysis Plan is documented in a separate Signature Document.

Table of Contents

Title page.....1

Abbreviations.....3

1. Introduction3

2. Study Objectives.....6

3. Study Design6

4. General Statistical Considerations9

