Part A. Each subject will be treated with the allocated dose of BAY 1093884 (X mg, Y mg or Z mg) for 12 weeks. These first 12 weeks will allow for primary safety evaluations of each dose.

[figure not shown]
Part B. Each subject will be treated for additional periods of 12 weeks in duration. After evaluation of the number of bleeds at the end of each 12-week period, subjects can be treated with the same dose or with the next higher opened dose level. The date when the last subject in Cohort 3 (Z dose) has completed Part B, will be the database cut-off date (i.e., primary completion date).

Extension part. After completion of Part B of the Z dose cohort, and upon DMC evaluation of safety data from the first 6 patients for 6 weeks in the dose Z cohort, all subjects will be invited to continue the treatment in an extension part, at the end of their ongoing Part B period. During the extension, all subjects will be evaluated (number of bleeds) every 12 weeks and escalated to the next higher opened dose, if dose escalation criteria are fulfilled (as per Part B). The extension part will continue, pending submission of safety and efficacy data to Health Authorities after 12 months from its start and every 12 months thereafter, until Marketing Authorization.

Any bleeding event, which should occur during the study (including the extension part) and which requires additional control, will be treated with the subject’s pre-assigned treatment (by-passing agent or replacement factor) prescribed by the Investigator pre-study.

Figure 1 shows a schematic overview of the study design.

Figure 1 Design overview

DMC = Data Monitoring Committee.

- Black boxes: Part A: Initial 12 weeks of treatment with BAY 1093884 (no escalation)
- Grey boxes: Part B: all subsequent groups of 12 weeks of treatment with BAY 1093884 (first escalation allowed)
- White boxes: Extension part with evaluations every 12 weeks (further escalations allowed)

Statistical Analysis Plan

Protocol No.: **BAY 1093884 / 19580**

Page: 8 of 19

Solid line arrows:	Option for dose escalation, if the next higher dose is approved and the subject meets the escalation criterion (>2 bleeds in Part A).
Dotted line arrows:	Option for dose escalation, if the next higher dose is approved and the subject meets the escalation criterion (>1 bleed in 12 weeks).

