4.5.2 Annualized bleed rate

Regarding the definition on the annualized bleed rate (see section 6.2.1) the following datetime will be used:

For annualized bleed rate for Part A, the first datetime of Part A will be the datetime of the first administration of study drug (Visit 2 – Start of BAY 1093884 treatment at the respective dose). The last datetime of Part A will be 1 minute before the datetime of the Visit 6 administration of study drug (the first administration of study drug in Part B). For subjects who discontinue the study during Part A, the last datetime of Part A is the datetime of the later of last visit and last administration of study drug.

For annualized bleed rate for each 12-week Part B period, the first datetime of the Part B period will be the datetime of the first administration of study drug in Part B (Visit 6) in case of first Part B period, or the datetime of the administration of study drug of Visit 7 or any subsequent 12-week visit. The last datetime of Part B will be 1 minute before the datetime of the administration of study drug of Visit 7 or the following subsequent 12-week visit. For subjects who discontinue the study during Part B, the last datetime of Part B is the datetime of the later of last visit and last administration of study drug.

For annualized bleed rate for period on dose initially received (DIR), the first datetime on DIR will be the datetime of the first administration of study drug (Visit 2 – Start of BAY 1093884 treatment at the respective dose). The last datetime on DIR will be 1 minute before the datetime of the administration of the next higher dose of study drug (Visit 6 or Visit 7). For subjects who discontinue prior to administration of the next higher dose or never met the dose-escalation criteria, the last datetime on DIR is the datetime of the later of last visit and last administration of study drug.

4.5.3 24 hours rule

Count no more than 1 bleed in a calendar day. If there is more than 1 bleed in a calendar day, to determine the bleed that gets counted, give priority to treated bleeds, spontaneous or trauma bleeds, then joint bleeds. Otherwise, count the first bleed in the day. Severity and treatment response will come from this selected bleed. Bleed site will be aggregated over all bleeds from that day. Regardless of which bleed is selected, the time of the first bleed in the day will be used. All other infusions in the day for treating bleeds will be considered follow-up infusions.

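### As extracted, the three ABR formulas in SAP 6.2.1 do not give bleeds per year, and the post-hoc plan, on its most natural reading, counts the escalation day under two doses (minor; descriptive ABR only)

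*SAP*

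**What the plan says.** **Main SAP.** Section 6.2.1 defines three annualized bleed rates (ABR): Part A, each 12-week Part B period, and the period on DIR. Each numerator is the bleed count times 365.25. In the text read from the PDF, the Part A denominator is "last datetime in Part A} - \text{first datetime in Part A}) \cdot 60 \cdot 60 \cdot 24" (braces and backslashes are formula markup). The other two have the same structure.

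Section 4.5.2 sets the windows as datetimes that do not overlap. Part A closes one minute before "the Visit 6 administration of study drug (the first administration of study drug in Part B". The DIR window closes one minute before the next higher dose or, without escalation, at the later of last visit and last administration.

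**Additional SAP of 10 March 2020, section 1.** This document is labelled post hoc. It counts inclusive calendar days, with denominator "last date in data scope} - \text{first date in data scope} + 1". It takes over the main SAP's counting rules ("the 24 hours rule as well as the 72 hours rule as described in SAP sections 4.5.3 and 4.5.4 apply") but does not refer to 4.5.2.

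- *Dose initially given:* the combined row covers the whole study time, and "Last date is the date of the intake of any study drug". There is no cut at escalation.
- *Dose actually given:* the plan is to "show for the dose actually given the annualized bleeding rates in Part B". For escalated subjects, "the last date in the data scope for a specific dose is the day the escalation into the higher dose group". The next sentence makes the day of escalation the first date for the new dose.

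The design-figure legend in SAP section 3 describes "Part B: all subsequent groups of 12 weeks of treatment with BAY 1093884 (first escalation allowed". Protocol 9.2.1.8 has a qualifying subject receive the higher dose at Visit 6 if the DMC has approved it.

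**The concern.** With 365.25 in the numerator, the denominator has to be a number of days. Converting seconds to days means dividing by 60·60·24, and the extracted formulas multiply instead. SAP 6.2.1 keeps ABR because it allows for unequal follow-up, so the denominator is the point of the measure.

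The post-hoc plan works in whole days and adds 1, so two adjoining windows must not share a date. If the escalation day belongs to both doses, one day of follow-up is used twice and a bleed on that day appears in two dose rows of a table meant for publication. The main SAP avoids this with its one-minute rule.

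**Working it through.** The documents state no ABR value to reproduce. As a check of scale, the post-hoc formula with its fixed 183 days gives 4 × 365.25 / 183 = 7.98 for four bleeds in six months. This agrees with the 8 or more bleeds a year that Protocol section 5 derives from the entry criterion, so the intended unit is bleeds per year.

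**1. Formulas in SAP 6.2.1.** Inputs: Part A is 12 weeks = 84 days, less one minute under 4.5.2, so 84 × 86,400 − 60 = 7,257,540 seconds. Three bleeds is an assumed count. SAP 4.1 names SAS; I assume that its datetime differences are in seconds and also try days.

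- Correct value: 3 × 365.25 / 84 = 13.04.
- As extracted, seconds: 3 × 365.25 / (7,257,540 × 86,400) = 1.7e-9, too small by 86,400².
- As extracted, days: 3 × 365.25 / (84 × 86,400) = 1.5e-4, too small by 86,400.
- Bar ending before the factor, seconds: [3 × 365.25 / 7,257,540] × 86,400 = 13.04, which is right.

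**2. Escalation day in the post-hoc plan.** Count the first dose as day 0. Part B starts on day 84, escalation is at Visit 7 on day 168, and follow-up on the new dose runs to day 251. Read the incomplete sentence as *day of* escalation.

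- Old dose: 168 − 84 + 1 = 85 days. New dose: 251 − 168 + 1 = 84 days. Sum 169.
- Real time: 251 − 84 + 1 = 168 days. The shared day is 1/85 = 1.2% of the old-dose window.
- With 2 bleeds, the old-dose ABR is 2 × 365.25 / 85 = 8.59, against 2 × 365.25 / 84 = 8.70 without the extra day.
- One bleed dated on day 168 adds 365.25 / 85 = 4.3 per year to the old dose and enters the new-dose row as well.
- Ending the old-dose window the day before gives 167 − 84 + 1 = 84 days, and 84 + 84 = 168.
- For escalation at Visit 6 (day 84), the day-before rule applied mechanically gives 83 − 84 + 1 = 0 days, so these subjects need an explicit statement.

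**3. Initial-dose rows: a different quantity, not a wrong one** (assumed counts).

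- Three bleeds in Part A, escalation at week 12. DIR rate: 3 × 365.25 / 84 = 13.04. As-assigned rate over 168 days with 0, 1 or 3 later bleeds: 6.52, 8.70 or 13.04.
- No escalation, 4 bleeds up to the last injection on day 119, last visit on day 126. Post-hoc window: 4 × 365.25 / 120 = 12.2. Window of 4.5.2: 4 × 365.25 / 126 = 11.6, or 5 × 365.25 / 126 = 14.5 with one further bleed. The difference in end date has no built-in direction.

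**The case against.** *The formula may be a reading artefact.* A flattened nested denominator or a misplaced fraction bar would produce exactly this text, three times over, and the intent is plain. This stands as a condition: the PDF has to be looked at before the formula is called an error in the plan. A rate near zero would also be noticed at once.

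*The escalation sentence is incomplete.* With *before* supplied instead of *of*, the windows would not overlap. That is so, but *of* is the more natural completion, and the next sentence uses that wording for the new dose. Either way the sentence needs repair. Even on the *of* reading, the bleed counts once in each of two rows, never twice in one.

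*One-day windows.* A reader might infer that a subject escalated at Visit 6 has an old-dose Part B window of 84 − 84 + 1 = 1 day, with an ABR of 0 or 365.25, the latter adding 365.25 / 8 = 45.7 to a mean over 8 subjects. The documents do not support this. The rows are by dose actually given in Part B, the Visit 6 injection is the first of Part B, and the escalated subject receives the higher dose at that visit. No old dose is given in Part B, so there is no old-dose row for him to enter. A per-subject mean over 8 is not specified for these rows either.

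*Undeclared change of definition.* A reader might also infer that the post-hoc windows silently replace those of 4.5.2. The plan is openly post hoc, writes out its own definitions, separates initial from actual dose and marks the combined row as the whole study time. An as-assigned summary is legitimate. What remains is that its name is close to DIR although it is not cut at escalation, which a footnote settles.

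**Conclusion.** Wrong as written, but minor. The formula finding depends on the PDF showing the layout that was extracted; if it does, none of the three formulas gives bleeds per year, by a factor of 86,400 (days) or 86,400² (seconds). The escalation-day finding depends on the *day of* reading. Its size is about 1.2% of an 85-day window, plus about 4.3 per year on the old dose for a bleed that falls on that one day. The bleed counts used here are illustrations.

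The reach is limited to descriptive ABR tables. The primary endpoint is safety, no hypothesis tests are planned, and no sample size rests on ABR. The initial-dose rows call for clearer labelling; they are not an error.

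**What to change.** 1. Check the fraction bar in the PDF of SAP 6.2.1. If the factor is in the denominator as extracted, print in all three places: ABR = bleeds × 365.25 / [(last datetime − first datetime, in seconds) / (60·60·24)].
2. In the additional SAP, complete the escalation sentence so that the old dose's window ends on the day before escalation. The whole escalation day then belongs to the new dose, as that plan's own start rule has it, and the windows no longer overlap, in line with SAP 4.5.2. State that subjects who receive the higher dose at Visit 6 contribute no old-dose Part B window.
3. Optional: say that the initial-dose window ends at the *last* intake of any study drug. Add a footnote that the combined and Part B initial-dose rows are as assigned, include time after escalation, and therefore differ from the DIR window of SAP 4.5.2.

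Cost: three formulas reprinted, one sentence corrected, one added and a footnote. No new data are needed.

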6.2.2 Subgroup analysis

CCI
[Redacted]

- [Redacted]
- [Redacted]
- [Redacted]

6.3 Pharmacokinetics/pharmacodynamics

All PK analyses will be based on the PK set.

Descriptive statistics for PK data will be presented as n, geometric mean, geometric standard deviation, geometric coefficient of variation, arithmetic mean, standard deviation (SD), median, minimum, and maximum.

The changes in PK parameters across the dose range studied may be assessed by comparisons of the above variables at each dose level. BAY 1093884 plasma concentrations will be plotted as a function of time for each subject according to dose.

Plots of summary data for each dose (geometric mean and arithmetic mean plasma concentrations at each time point) will also be presented on both linear and logarithmic scales. BAY 1093884 plasma levels may also be plotted to evaluate the correlation of plasma levels with safety and other endpoints.

PD parameters will be analyzed descriptively and with statistical models as appropriate.

6.4 Safety

In accordance with the primary objective of the study, which is the assessment of the safety and tolerability of multiple subcutaneous doses of BAY 1093884 in subjects with hemophilia A or B with or without inhibitors, the primary variables of the study are the following:

- Incidences of drug-related AEs, SAEs, adverse events of special interest (AESIs), and clinically relevant abnormal laboratory values.

Hypersensitivity reactions, thromboembolic and thrombotic microangiopathic events are defined as AESIs.

In addition, the following safety variables are also of particular interest:

- Incidences of injection site reactions (ISRs)
- Incidences of binding and neutralizing antibodies against BAY 1093884

6.4.1 Adverse events

The investigator has to record on the respective CRF pages all adverse events occurring in the period between the signing of the informed consent form and the end of the follow-up phase. The original terms used by investigators to report AEs via the CRFs will be coded using the Medical Dictionary for Regulatory Activities (MedDRA).

For each AE, the number and percentage of subjects who experienced at least 1 occurrence of the given event will be tabulated according to the affected primary system organ class (SOC) and preferred term (PT) by dose cohort and dose actually received. A total column will be included in all safety summaries.

Frequency tables, showing an overall summary of number of subjects with drug-related AEs, SAEs and AESIs will be given, and will include the following information:

- maximum intensity for any AE,
- AE related deaths,
- AE resulting in permanent discontinuation of study drug,

- treatment emergent AE.

AEs will be considered treatment-emergent if they begin after the first administration of study drug and they do not start after more than 30 days after the last administration. Determination of whether or not an event is treatment-emergent will be derived after the missing or incomplete AE start date is imputed. Inhibitors will be defined as treatment-emergent if they develop after first study drug application. Imputation rules for missing and incomplete AE start are described in section 4.3.

The severity or intensity of an AE should be graded according to the National Cancer Institute Common Terminology Criteria for Adverse Events (NCI CTCAE) version 5.0. If no exact matching code is available in NCI CTCAE version 5.0, the following guidance should be used:

- CTCAE grade 1: Mild
- CTCAE grade 2: Moderate
- CTCAE grade 3: Severe and/or disabling AE
- CTCAE grade 4: life-threatening and/or intervention needed
- CTCAE grade 5: resulting in death (fatal)

A similar table showing overall summary information of AEs during screening will be given.

In addition, frequency tables will summarize the number of subjects with injection site reactions.

Similar to 6.2, frequency tables will summarize the number of subjects with

- any event during Part A,
- any event during each 12-week Part B period
- any event during combination of these periods.

This will also include tabulation by dose actually received.

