A DMC will review key safety data and dose recommendation before recommending escalation to the next dosing cohort.

At a minimum, safety/PK/PD data from 6 subjects completing 6 weeks in Cohort 1 (Dose X) are needed to open Cohort 2 (Dose Y). All available safety information will be taken into consideration. This may include data from the 2 additional subjects in the cohort who may

not have reached the 6 weeks or additional data from any of the first 6 subjects who may have been dosed for longer than 6 weeks. This guideline will apply to further cohorts as well. All available safety information from ongoing subjects will be used for safety evaluation in opening the next dose cohort. This includes safety data also from the subjects who may have escalated from a previous cohort. Details on the criteria for dose escalation can be found in the DMC charter.

Any subject from dose cohort X can escalate to the dose level Y only after dose Y has been opened (i.e., after data from 6 subjects is available after 6 weeks of treatment), the subject in dose cohort X has been treated for at least 12 weeks and meets the individual dose escalation criteria described in the study design section. Equally, any subject from dose cohort Y can escalate to the dose level Z only after dose Z has been opened and the subject in dose cohort Y has been treated for at least 12 weeks at dose level Y.

The current PK/PD model will be updated with data from a minimum of 6 subjects dosed for 6 weeks in each cohort and will include any additional data from all ongoing subjects prior to decision for opening a cohort. This updated model will be used to propose the next dose level for the new cohort.

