10.3.2 Extent of exposure

Extent of exposure to the study and reference drug (rescue medication, pre-study medication), including injection characteristics, will be summarized for all subjects receiving any amount of drug.

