10.3.5 Analysis of safety

The safety profile will be analyzed using the SAF population and safety data collected during Part A. Vital signs, AEs, and laboratory data will be analyzed by descriptive statistics, such as summary statistics and frequency tables. All AEs will be tabulated according to the affected system organ class and preferred term, as coded by the medical dictionary for regulatory affairs (MedDRA).

Further safety analyses will include all safety data available at the time when Cohort 3 will have completed Part A and Part B of the study. For each subject, safety variables will be

analyzed by study part and the respective visits and by dose actually received, both by dose cohort and by study medication actually received during the respective interval. This includes safety analyses by dose last received.

The evaluation of safety data and the version of MedDRA used for coding will be detailed in the SAP.

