10.5 Planned interim analyses

After all subjects still participating in the study have completed Part A and at least one 12-week Part B period (primary completion) of the study, all dose levels will be assessed including clinical safety, routine safety laboratory, hemostasis and thrombosis markers as per PK/PD assessment and clinical efficacy.

For safety, AEs will be assessed for all subjects per dose level. In case of comparable clinical safety, the routine lab findings will be evaluated. In case of comparable clinical and laboratory safety, thrombosis and hemostasis markers will determine safety evaluation.

For efficacy, the number of subjects without spontaneous bleeds requiring treatment in addition to BAY 1093884 will be assessed; all other efficacy variables will be assessed for the dose levels observed.

11. Data handling and quality assurance

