4.4 Interim Analyses and Data Monitoring

An independent Data Monitoring Committee will review safety data according to the DMC charter. No alpha adjustment is required. No interim efficacy analysis is planned.

After all subjects still participating in the study have completed Part A and at least one 12-week Part B period (primary completion) of the study, all dose levels will be assessed including clinical safety, routine safety laboratory, hemostasis and thrombosis markers as per PK/PD assessment and clinical efficacy.

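### AE tables that pool follow-up show only crude percentages although time on dose differs by design, and the per-dose AE comparison at primary completion is not tied to Part A

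*SAP*

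**What the plan says.** **Measure.** SAP 6.4.1 states: "For each AE, the number and percentage of subjects who experienced at least 1 occurrence of the given event will be tabulated", by dose cohort and by dose actually received. It adds tables for Part A, for each 12-week Part B period, and for "any event during combination of these periods". Neither the Protocol, the SAP nor the 2020 additional SAP plans an AE rate per unit of exposure or a time-to-event summary.

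**Main window.** Protocol 5 assigns the primary safety evaluation of each dose to the 12 weeks of Part A. Protocol 10.3.5 agrees: "The safety profile will be analyzed using the SAF population and safety data collected during Part A". It then plans further analyses of all safety data up to the Cohort 3 cut-off, "analyzed by study part and the respective visits and by dose actually received".

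**Exposure.** Under Protocol 10.3.2, exposure "will be summarized for all subjects receiving any amount of drug", but this is not linked to AE counts. The SAP has no extent-of-exposure section.

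**Comparison at primary completion.** Protocol 10.5 says: "For safety, AEs will be assessed for all subjects per dose level". Laboratory findings come next if clinical safety is judged similar. SAP 4.4 says that "all dose levels will be assessed including clinical safety". Neither names a window or a measure for AEs.

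**Bleeds.** SAP 6.2.1 adds annualized rates because follow-up may differ between subjects. AEs have no counterpart.

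**The concern.** A crude percentage is the share of subjects with an event by the end of their observation, so it rises with time observed. The design makes that time unequal. Y opens only after six X subjects have completed 6 weeks, Z follows the same process, and all cohorts share one cut-off. Subjects who escalate stop adding time to the lower dose and bring short follow-up to the higher one.

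Safety by dose is the primary objective and one of the two stated inputs to the Phase 3 dose. In a pooled table, a difference between doses, or the lack of one, can partly reflect time on dose. The Part A table guards against this, but the sections on the comparison at primary completion do not say that it is the table to use.

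**Working it through.** **The plan's own figures.** 3 cohorts × 8 = 24 subjects, and 12 + 12 = 24 weeks for Cohort 3; both reproduce. The documents give no AE rate and no threshold for similar safety, so the event rates below are assumptions.

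**Step 1: time on dose at cut-off.** Inputs: 6 weeks of data before each cohort opens (Protocol 5 and 7.4.1.1), and a cut-off when the last Cohort 3 subject completes 24 weeks (Protocol 5, Primary completion). Assume no delay, no dropout, and all 8 subjects of a cohort starting together. Cohorts then start at weeks 0, 6 and 12, and the cut-off is week 12 + 24 = 36.

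- Overall: X 36, Y 36 − 6 = 30, Z 36 − 12 = 24 weeks.
- Part B as a whole (subtract 12): 24, 18 and 12 weeks.
- Patient-years for 8 subjects: 8 × 36/52.18 = 5.52; 8 × 30/52.18 = 4.60; 8 × 24/52.18 = 3.68.
- An assumed delay of 4 or 12 weeks per cohort opening widens this to 44/34/24 or 60/42/24 weeks.
- If X subjects 7 and 8 start 6 or 12 weeks late, the X mean falls to 34.5 or 33 weeks.

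**Step 2: crude share with equal true risk, no escalation.** Share = 1 − exp(−r × t/52.18), where r is first events per patient-year and t is weeks on dose.

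| r (assumed) | X, 36 wk | Y, 30 wk | Z, 24 wk | X/Z |
|---|---|---|---|---|
| 0.5 | 29.2% | 25.0% | 20.5% | 1.42 |
| 1 | 49.8% | 43.7% | 36.9% | 1.35 |
| 2 | 74.8% | 68.3% | 60.1% | 1.24 |

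At r = 1 this is 4.0, 3.5 and 2.9 of 8 subjects. With X subjects 7 and 8 late, X is 48.3% or 46.6%. For Part B as a whole at r = 1, the same formula at 24, 18 and 12 weeks gives 36.9%, 29.2% and 20.5%.

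**Step 3: a difference that would be hidden.** Equal shares arise when r × t is equal. Since 1.5 × 24 = 36, a rate truly 1.5 times higher at Z would show as the same percentage as at X.

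**Step 4: escalation, counted by dose received, r = 1.** X to Y occurs at X week 12, leaving 12 weeks on X. Those subjects stay on Y for 24 weeks, or move to Z after 12 and have 12 weeks there. Y to Z occurs at Y week 12, giving 12 weeks on Y and 18 on Z.

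| Scenario | n X/Y/Z | Mean weeks | Share X/Y/Z |
|---|---|---|---|
| None | 8/8/8 | 36/30/24 | 50/44/37% |
| Moderate: 4 of 8 X, 2 of those again, 2 of 8 Y | 8/12/12 | 24/23/21 | 35/35/33% |
| Heavy: 8 of 8 X, 4 of those again, 4 of 8 Y | 8/16/16 | 12/19.5/19.5 | 21/30/31% |

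In the heavy case Z/X is 1.50 (1.56 at r = 0.5, 1.40 at r = 2).

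**Step 5: escalation, counted by assigned cohort.** SAP 4.1 leaves out escalated subjects' Part B data. If 4 of 8 X subjects escalate at week 12, X is (4 × 49.8 + 4 × 20.5)/8 = 35.2%, against 36.9% for Z without escalation. If 6 of 8 escalate, X is (2 × 49.8 + 6 × 20.5)/8 = 27.9% against 36.9%. The direction reverses here too.

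**The case against.** The strongest defence is that the plan already has the right window. Protocol 5 and 10.3.5 make Part A the main safety evaluation and call the all-data analyses further work. SAP 4.1 also sets a general rule that data are shown by Part A and Part B, so the organ-class and summary tables, whose own paragraphs give no period, need not pool everything. This stands. The Part A table and the single 12-week Part B tables have equal planned length. So does Part A plus the first Part B period (24 weeks) for subjects who stay on their dose. It does not cover the combination tables beyond that, Part B as a whole, or the all-data analyses to cut-off. Nor does it make Protocol 10.5 or SAP 4.4 point to Part A.

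The second defence is size. The no-escalation gap is about one subject in 8, and moderate escalation nearly removes it. For rare events it is negligible: at an assumed 0.1 per patient-year, X is 6.7% and Z 4.5%, or 0.17 of a subject. Phase 1 reported no SAE in 32 subjects. Events clustered soon after the first dose are less affected. Safety is descriptive, without tests, and all data are listed. This stands as well, and it limits the priority.

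A reader might infer that all between-dose safety evidence is distorted by exposure, or that the pooled tables always count against the lower dose. The documents support neither. The main window is equal by design, and Steps 4 and 5 show that the direction depends on how many subjects escalate.

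**Conclusion.** The point holds for the pooled AE tables and for the silence of Protocol 10.5 and SAP 4.4 on the window. It does not reach the main safety evaluation. Time on dose differs by at least 36/30/24 weeks overall and 24/18/12 weeks in Part B without escalation, and the planned measure takes no account of it. The resulting distortion runs from almost none to a ratio of about 1.5 between X and Z, in either direction.

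The week counts follow from the design rules, assuming no delay or dropout and cohorts that start together. The percentages also need the assumed constant event rates and escalation patterns. SAP 6.2.1 already accepts the principle for bleeds. This is a cheap improvement of low to moderate priority.

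**What to change.** 1. In SAP 4.4, and in Protocol 10.5 at the next amendment, state that the between-dose AE comparison uses the Part A window, with pooled data as support.
2. In SAP 6.4.1, add one supportive table beside the pooled crude percentages for drug-related AEs, SAEs and AESIs. For each dose give patient-years, and subjects with a first event on that dose per patient-year at risk, with exact Poisson 90% intervals.
   - Time at risk restarts at escalation and is censored at the first event on that dose.
   - SAP 6.4.1 counts events as treatment-emergent up to 30 days after the last administration; events and time in that tail go to the last dose received.
   - If total events per patient-year are shown, give no Poisson interval, because repeated events cluster within subjects.
3. Repeat the SAP 6.2.1 caution that dose received after Part A depends on post-baseline events. Person-time does not remove that selection.

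**Cost.** Two sentences and a little programming from dosing, escalation and onset dates already recorded. No planned table is replaced. The rates assume roughly constant risk, and the intervals are wide. Three events in 3.68 patient-years (full Cohort 3 time, before censoring) give 3/3.68 = 0.82 per patient-year, with a 90% interval of 0.22 to 2.11. The table therefore shows exposure and direction but cannot separate a 1.5-fold difference.
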